9. A urine dipstick should be performed at each of the visits indicated. A complete microscopic urine assessment is required only if a urine dipstick is abnormal.
10. Virology assays should be performed at an IMPAACT/VQA approved laboratory. The Abbott platform MUST be used for the HIV-1 RNA.
11. Lymphocyte subsets should include CD4 and CD8.
12. Subjects should have taken ETR for at least 7 consecutive days prior to the intensive PK, without missing a dose. Intensive PK should be scheduled so that a witnessed dose of ETR is taken approximately 12 hours after the previous dose. PK dosing within a range of 11 to 13 hours after the previous dose is acceptable. The team suggests that an indwelling catheter such as a saline or heparin lock be used for the intensive PK. Once the subject has arrived at the clinic, he/she should be offered a breakfast appropriate for their age. Within 30 minutes following breakfast, the PK medications should be administered followed by the PK sampling at the specified time points. If the subject vomits within 15 minutes of taking study drug, the dose should be repeated. Subjects may resume food intake 2 hours after their dose of ETR at the intensive PK visit. One (1) mL of blood will be collected at the following time points: pre-dose, 1, 2, 4, 6, 9 and 12 hours post dosing. To allow for some flexibility, the 9-hour sample can be collected with a window

of 8-10 hours post-dose and the 12 hour sample with a window of 11 to 13 hours. If necessary, the 1-hour post-dose sample and/or the 9-hours post-dose sample can be deleted to reduce the amount of total blood drawn from 7 samples over 12 hours to 5 or 6 samples, over 12 hours.

If a subject requires individual dose adjustment for low or high AUCs, they will be asked to return to clinic to have an intensive PK evaluation between Day 7-14 on the new dose.

If a mini or full cohort fails, the failing subjects may have their ETR dose adjusted. In those cases, subjects will be asked to return to clinic to have a truncated intensive PK between Day 7-14 on the new dose with samples collected at the following time points: pre-dose, 2, and between 3-5 hours post dosing.

Note that a repeat EKG is required at the time of a PK visit required for any of the reasons described above.

13. 1.0mL of blood will be collected for each of the population pharmacokinetic samples. NOTE: An absolute minimum of 0.5 mL is necessary for population PK sample.

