APPENDIX IC: SCHEDULE OF EVALUATIONS – Cohort III

	Study Visits												
	Screen ¹	Entry (Day 0)	Day 14 Intensive PK Visit	Week 4	Week 8	Week 12	Week 16	Week 24	Week 32	Week 40	Week 48	Early Study D/C	Virologic failure ²³
Visit Windows			±4 days	±1wk	±1wk	±1wk	±2wk	±2wk	±2wk	±2wk	±2wk		
CLINICAL EVALUATIONS													
Informed Consent	X												
History and Physical ²	X	X	X	X	X	X	X	X	X	X	X	X	X
CDC Classification	X	X				X		X			X	X	X
Adherence / Pill Count Form			X ¹⁷	X ¹⁷	X	X	X	X	X	X	X	X ¹⁷	X
Adherence Phone Call			X ¹⁸										
Electrocardiogram ³	X		X ^{13, 19}										
STUDY DRUG													
Distribution of Study Drug ⁴			X				X		X	X			
LABORATORY EVALUATIONS													
Hematology ⁵	0.5mL	0.5mL	0.5mL	0.5mL	0.5mL	0.5mL	0.5mL	0.5mL	0.5mL	0.5mL	0.5mL	0.5mL	0.5mL
Chemistries ⁶	1mL	3mL	1mL	1mL	1mL	3mL	1mL	3mL	1mL	1mL	3mL	1mL	1mL
Cholesterol/triglycerides ⁷		X				X		X			X		
Coagulation assays ⁸	2mL					2mL		2mL					
Urinalysis ⁹	X	X						X			X	X	X
Virology Evaluations													
HIV-1 RNA PCR ¹⁰	3mL	3mL ¹⁶	3mL	3mL	3mL	3mL	3mL	3mL	3mL	3mL	3mL	3mL	3mL
CYP genotyping ¹¹		X ¹⁶											
HIV genotype & phenotype	4mL ¹⁵											4mL	4mL
Immunology Evaluations													
Lymphocyte subset ¹²	1mL	1mL		1mL	1mL	1mL	1mL	1mL	1mL	1mL	1mL	1mL	1mL
Pellets/plasma for storage								2mL ¹¹			2mL ¹¹		
Pharmacology Evaluations													
Intensive Pharmacokinetics ¹³			3.5mL										
Population PKs ¹⁴				0.5mL ²⁰	0.5mL ²¹	0.5mL ²²		0.5mL ²⁰			0.5mL ²²		0.5mL ²⁴
TOTAL BLOOD VOLUME	11.5mL	7.5mL	8.0mL	6.0mL	6.0mL	10.0mL	5.5mL	12.0mL	5.5mL	5.5mL	10.0mL	9.5mL	10.0mL

Footnotes

1. Informed consent must be obtained prior to performing Screening evaluations. The entry (Day 0) evaluations should be completed within 60 days following screening. For children of low weight, the screening laboratory evaluations may be split over 2 visits. Safety labs and lymphocyte subsets should be obtained at the first timepoint and HIV RNA and HIV genotyping and phenotyping a week later.
2. A complete history and physical should be done at screening. At subsequent visits, an interim history and physical should be performed. This should include history (including occurrence of adverse events since last study visit and any HIV-1 associated conditions) and physical exam (including height [without shoes], weight [with minimal clothing], vital signs [temperature, pulse, respirations, blood pressure and head circumference]).

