8. Coagulation assays should include PT, PTT and INR. Required only from study sites with access to laboratories with existing coagulation testing capabilities for the tests as determined by IMPAACT.
9. A urine dipstick should be performed at each of the visits indicated. A complete microscopic urine assessment is required only if a urine dipstick is abnormal.
10. Virology assays should be performed at an IMPAACT/VQA approved laboratory. The Abbott platform MUST be used for the HIV-1 RNA.
11. Collection of blood for genotyping and stored specimens may be omitted for the youngest infants if the necessary volume of blood is difficult to draw. Note that CYP genotyping and viral load PCR can be run from the same blood sample; see footnote 16.
12. Lymphocyte subsets should include CD4 and CD8 assays.
13. Subjects should have taken ETR for at least 7 consecutive days prior to the intensive PK, without missing a dose. Intensive PK should be scheduled so that a witnessed dose of ETR is taken approximately 12 hours after the previous dose. PK dosing within a range of 11 to 13 hours after the previous dose is acceptable. The team suggests that an indwelling catheter such as a saline or heparin lock be used for the intensive PK. Once the subject has arrived at the clinic, he/she should be offered a breakfast appropriate for their age. Within 30 minutes following breakfast, the PK medications should be administered followed by the PK sampling at the specified time points. If the subject vomits within 15 minutes of taking study drug, the dose should be repeated. Subjects may resume food intake 2 hours after their dose of ETR at the intensive PK visit. One (1) mL of blood will be collected at the following time points: pre-dose, 1, 2, 4, 6, 9 and 12 hours post dosing. To allow for some flexibility, the 9-hour sample can be collected with a window

of 8 to 10 hours post-dose and the 12 hour sample with a window of 11 to 13 hours. If necessary, the 1-hour post-dose sample and/or the 9-hours post-dose sample can be deleted to reduce the amount of total blood drawn from 7 samples over 12 hours to 5 or 6 samples, over 12 hours.

If a subject requires individual dose adjustment for low or high AUCs, they will be asked to return to clinic to have an intensive PK evaluation between Day 7-14 on the new dose.

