If a mini or full cohort fails, the failing subjects may have their ETR dose adjusted. In those cases, subjects will be asked to return to clinic to have a truncated intensive PK between Day 7-14 on the new dose with samples collected at the following time points: pre-dose, 2, and between 3-5 hours post dosing.

Note that a repeat EKG is required at the time of a PK visit required for any of the reasons described above.

14. 0.5mL of blood will be collected for each of the population pharmacokinetic samples. NOTE: An absolute minimum of 0.5 mL is necessary for population PK sample.
15. Cohort III subjects must wait until HIV-1 genotyping results are available BEFORE they can start ETR and OBR.
16. Wherever possible, the CYP genotyping and viral load PCR can be run from the same blood sample. The blood draw should be collected and spun down to isolate pellets for PBMCs (for CYP genotyping) and the plasma can be used for the viral load. Otherwise, a separate blood tube should be drawn.
17. Sites should also perform the palatability assessment at these visits.
18. Subjects must have taken their ETR doses as directed by the study physician, for 7 days prior to the intensive PK visit, without any missed doses. Sites are strongly encouraged to call the subject, the day before the intensive PK visit, so that the site staff can confirm that the subject has not missed any doses in the previous 7 days. If the subject has missed a dose, the PK visit must be re-scheduled within the Day 14 (\pm 4 days) window.
19. The ECG at the intensive PK visit should be collected following the 4 hour blood draw. This time point is generally when the drug level is at its highest.
20. At weeks 4 and 24, one sample should be timed to fall within a window of 1 to 4 hours following a dose of etravirine.
21. At week 8, one sample should be timed to fall within a window of 4 to 8 hours following a dose of etravirine.
22. At weeks 12 and 48, one sample should be timed to fall within a window of 8 to 12 hours following a dose of etravirine. (See Section 9.36 for additional information).
23. If a subject is experiencing virologic failure (as defined in section 6.3), a visit to confirm failure must be conducted between 1 to 4 weeks of the initial suspected failure or rebound.
24. At virologic failure, one sample may be collected at any time following a dose of etravirine.

For insufficient blood draws, priorities are as follows:

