Hematology (0.5mL); Chemistry (1mL); Pharmacology (intensive [3.5mL] or population [0.5mL]); Virology (HIV-1 RNA PCR – 3mL); Resistance testing (HIV genotype and phenotype – 4mL); Lymphocyte subsets (1mL); CYP genotyping (2mL); Cholesterol / triglycerides (2mL); Coagulation assays (2mL); Plasma/cell pellet for storage (2mL)

APPENDIX ID: SCHEDULE OF EVALUATIONS FOR FOLLOW UP OF SUBJECTS WHO DISCONTINUE ETRAVIRINE (OFF STUDY DRUG – ON STUDY)

Week 4 post ETR discontinuation (± 2 weeks)	
CLINICAL EVALUATIONS	
History and Physical ¹	X
CDC Classification	X
LABORATORY EVALUATIONS	
Hematology ²	1mL
Chemistries ³	3mL
Cholesterol / triglycerides ⁴	1mL
Virology	
HIV-1 RNA PCR ⁵	3mL
Immunology	
Lymphocyte subsets ⁶	2mL
TOTAL BLOOD VOLUME (mL)	10mL

NOTE: Subjects who are withdrawn from study drug within the first 48 weeks of study will not enter long term follow-up, but will return to clinic 4 weeks after ETR discontinuation, as per Appendix ID. Subjects with AEs will be followed until satisfactory clinical resolution (i.e. value returns back to subjects baseline value) or stabilization (to be agreed upon with the sponsor). All grade 3 and grade 4 laboratory abnormalities as well as any laboratory abnormalities resulting in an increase of 2 DAIDS Grades from baseline, will be followed until return to baseline or within 1 Grade from baseline. If an AE resolves within 4 weeks of discontinuation of ETR, the subject should still return for the final 4 week study visit.

Footnotes

1. History (including occurrence of adverse events since last study visit and any HIV-1 associated conditions) and physical exam (including height [without shoes], weight [with minimal clothing], vital signs [temperature, pulse, respirations and blood pressure]).
2. Hematology tests should include complete blood count (CBC), differential and platelets.
3. Electrolytes (sodium, potassium, and HCO₃), glucose, creatinine, lipase, phosphorus, and LFTs. LFTs should include total bilirubin, indirect bilirubin, direct bilirubin, alkaline phosphatase, AST, ALT, and albumin. If indirect bilirubin is not reported by the site laboratory, it should be calculated at the site and documented.
The following (listed in order of preference) should be used to determine the upper limit of normal (ULN) values for indirect bilirubin.
 - a. "ULN" values reported by the laboratory report for the test, or
 - b. "ULN" values routinely used/established by the site, or

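### Appendix IC footnote 13 tells sites to draw 1 mL per intensive PK sample in Cohort III (7 mL), but the schedule provides for 3.5 mL; it should read 0.5 mL

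*Protocol*

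**What the plan says.** Appendix IC of the Protocol is the schedule of evaluations for Cohort III (2 months to under 1 year). It gives the intensive PK blood volume in four places.

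- **Footnote 13**, attached to the intensive PK row: "One (1) mL of blood will be collected at the following time points: pre-dose, 1, 2, 4, 6, 9 and 12 hours". It lets sites leave out the 1-hour and/or 9-hour sample, to "reduce the amount of total blood drawn from 7 samples over 12 hours to 5 or 6 samples, over 12 hours".
- **The intensive PK row** gives 3.5 mL on Day 14.
- **The total blood volume row** gives 8.0 mL on Day 14.
- **The priorities for insufficient draws** list "Pharmacology (intensive [3.5mL] or population [0.5mL" mL for the two kinds of PK sampling.

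The next footnote, on population PK, has a volume specific to the infants: "0.5mL of blood will be collected for each of the population pharmacokinetic samples". The matching footnote in Appendix IB, for Cohort II, reads "1.0mL of blood will be collected for each of the population pharmacokinetic samples".

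Footnote 13 also covers children whose dose is individually adjusted: "they will be asked to return to clinic to have an intensive PK evaluation between Day 7-14 on the new dose". Section 9.33 lists the sampling times but no volume.

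**The concern.** Footnote 13 is the only place in Appendix IC that states a volume per time point for the intensive PK, so staff filling tubes one at a time would look there. It conflicts with the row it annotates. Sites therefore hold two instructions that differ by a factor of two, for the youngest and smallest children in the trial.

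The repeat intensive PK is more exposed to the error. Section 9.34 requires one after every individual dose adjustment not caused by weight gain, and Section 9.33 lets the team request one if a PK visit went wrong. The schedule has no column for that visit, so no table cell shows 3.5 mL for it. Repeats do occur: Section 1.32 reports that two of the first six children in the trial had PK-driven dose increases, although that was in Cohort I on a dose since replaced.

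The protocol itself treats blood volume as a concern in this cohort. Footnote 1 of Appendix IC says: "For children of low weight, the screening laboratory evaluations may be split over 2 visits". That allowance to split a draw covers screening only, not Day 14.

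**Working it through.** **Inputs.** All volumes are from the Appendix IC table for Day 14: hematology 0.5 mL, chemistries 1 mL, HIV-1 RNA 3 mL, intensive PK 3.5 mL, stated total 8.0 mL. Footnote 13 gives seven samples, reducible to six or five, at 1 mL each.

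**Step 1: reproduce the plan's own total.** 0.5 + 1 + 3 + 3.5 = 8.0 mL, as stated. The other 12 visit totals in the Cohort III table also re-add exactly, so the table is internally sound and was not garbled in extraction.

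**Step 2: apply the footnote.** PK volume = number of samples × volume per sample. Day 14 total = 0.5 + 1 + 3 + PK volume.

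| Samples | mL per sample | PK volume (mL) | Day 14 total (mL) |
|---|---|---|---|
| 7 | 1.0 | 7.0 | 11.5 |
| 6 | 1.0 | 6.0 | 10.5 |
| 5 | 1.0 | 5.0 | 9.5 |
| 7 | 0.5 | 3.5 | 8.0 |

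No permitted scheme at 1 mL gives 3.5 mL. Seven samples at 0.5 mL match the row, the total and the priority list exactly.

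**Step 3: size of the discrepancy.**

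- PK draw: 7.0 / 3.5 = 2.00 (+100%). With six or five samples: 6.0 / 3.5 = 1.71 and 5.0 / 3.5 = 1.43.
- Day 14 total: 11.5 / 8.0 = 1.44 (+44%, or 3.5 mL).
- Per kg on Day 14, as written against as intended. The weights are assumed: 6 and 10 kg are band edges in Dosing Table 2, and 4 kg stands for an infant in the lowest band.
  - 4 kg: 11.5/4 = 2.9 against 8.0/4 = 2.0 mL/kg
  - 6 kg: 11.5/6 = 1.9 against 8.0/6 = 1.3 mL/kg
  - 10 kg: 11.5/10 = 1.15 against 8.0/10 = 0.80 mL/kg
- With one repeat intensive PK: PK blood 7.0 + 7.0 = 14.0 against 3.5 + 3.5 = 7.0 mL. Entry + Day 14 + Week 4 + repeat PK: 7.5 + 11.5 + 6.0 + 7.0 = 32.0 against 7.5 + 8.0 + 6.0 + 3.5 = 25.0 mL (+28%).

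**Step 4: which figure is the error?** The same sentence appears in Appendices IA and IB. There 7 × 1 mL = 7 mL agrees with the row and with the Day 14 total: 1 + 2 + 3 + 7 = 13 mL. Appendix IC halves the other routine volumes: hematology 1 to 0.5 mL, chemistries 2 to 1 mL (at visits without lipids), lymphocyte subsets 2 to 1 mL, population PK 1.0 to 0.5 mL. The intensive PK row was halved as well, from 7 to 3.5 mL. Only the sentence in footnote 13 was left unchanged.

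**The case against.** The contradiction is not in dispute; its weight is. The strongest case for treating it as a minor slip runs as follows.

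- **The intended value is visible.** Three places agree on 3.5 mL, and a site planning the visit sees the table before the footnote. This is true and makes the error less likely to be acted on. The footnote is still the sole per-tube instruction.
- **The priority list is not tied to a visit**, so its 3.5 mL also applies to a repeat intensive PK. This stands: the repeat is not governed by the footnote alone. But that list is meant for draws that fall short, not for planning a full one.
- **Day 14 has some relief**, through the optional deletions and the priority order. This also stands, but at 1 mL per sample the deletions leave 5 or 6 mL, still above 3.5 mL.
- **No breach is shown.** The documents give no limit per kg or per visit. Even 11.5 mL equals the screening total and is below Week 24 (12.0 mL). Accepted, with two qualifications: screening may be split, and by Week 24 the infants are older and the 2 mL storage sample may be omitted for the youngest.
- **The 32.0 mL sum is conditional.** It needs an individual dose adjustment and normally spans more than a month. The ordinary effect is 3.5 mL extra, once per infant, with 12 infants planned.
- **The figure of 0.5 mL is inferred.** No sentence states it for intensive PK, and the stated 0.5 mL minimum applies to population PK samples. Laboratory confirmation is therefore sensible. A volume for the truncated draw is added detail, since no appendix gives one.

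None of this makes the footnote correct or reconciles it with the table.

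**Conclusion.** The concern holds: footnote 13 is wrong as written. It orders 7 mL where the schedule provides for 3.5 mL, and it lifts the Day 14 draw from 8.0 to 11.5 mL (+44%) in infants from 2 months of age. It should be corrected because it is an operative blood-draw instruction, even though the harm is limited to excess blood volume and a confusing order to sites. The direction of the correction rests on inference: 0.5 mL is the only equal per-sample volume that gives 3.5 mL over seven samples, and it matches the population PK volume in the next footnote. The per-kg figures rest on assumed weights and the cumulative figure on one repeat PK. Sample size, AUC, virologic and CD4 analyses are unaffected.

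**What to change.** In Appendix IC, footnote 13, replace 1 mL with 0.5 mL per time point. Add that 0.5 mL per sample also applies in Cohort III to repeat intensive PK and to the three-sample truncated PK. Before issuing it, have the pharmacology laboratory confirm that 0.5 mL is enough for the intensive PK assay. The row, the Day 14 total and the priority list need no change. The cost is one number and one added sentence, sent to sites as a clarification memo.

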APPENDIX II: PLANNED LABORATORY TESTING ON COLLECTED SPECIMENS

Specimen	Assay	Investigator / Laboratory	Notes
EDTA blood	Hematology	Local IMPAACT laboratory	
EDTA blood	Lymphocyte subsets	Local IMPAACT laboratory	
Serum or LiHeparin (site /method dependent)	Chemistries/ cholesterol /triglycerides	Local IMPAACT laboratory	
EDTA plasma	HIV-1 RNA PCR (viral load)	Local IMPAACT laboratory	Laboratory must be using Abbott platform and be VQA certified
EDTA plasma	Resistance Testing (Genotyping) SCREENING Only	U.S. Sites: University of Washington Seattle WA	Specimens should be shipped in real time
		Africa Sites: Contract Laboratory Services, Johannesburg, SA	Specimens should be shipped in real time
		South America Sites: FioCruz, Brazil	Specimens should be shipped in real time
		Thailand Sites: PHPT Laboratory Chiang Mai, Thailand	Specimens should be shipped in real time
		India Sites: Testing will be performed in country at a DAIDS network laboratory	Specimens should be shipped in real time
EDTA plasma	Resistance Testing (Phenotyping) SCREENING Only	U.S. / Brazil Sites: Monogram Sciences	Specimens should be shipped in real time
		All Other Sites: BRI Repository	Specimens should be shipped in real time and will 'pass-through' BRI to Monogram
EDTA Plasma	Resistance Testing (Genotyping) VIROLOGIC FAILURE / EARLY STUDY D/C	U.S. Sites: University of Washington Seattle WA	Specimens should be batch shipped quarterly
		All Other Sites: BRI Repository	Specimens should be batch shipped quarterly and will 'pass- through' BRI to Monogram
EDTA Plasma	Resistance Testing (Phenotyping) VIROLOGIC FAILURE / EARLY STUDY D/C	U.S. / Brazil Sites: Monogram Sciences	Specimens should be batch shipped quarterly
		All Other Sites: BRI Repository	Specimens should be batch shipped quarterly

APPENDIX III: ETRAVIRINE DRUG DOSING TABLE FOR ORAL TABLET

Note: If the protocol team determines that a revised starting dose of etravirine is needed, modeling and simulation will be used (incorporating all available PK data at that time) to propose a revised weight-based dosing table for ETR for which the calculated chance of success for a given age cohort (i.e., geometric mean AUC_{12h} between 60 and 150% of adults) will be at least 80%. For this, available doses of ETR (based on available formulations of 100 mg tablet and 25 mg scored tablet) between 12.5 mg orally twice daily (BID) and 200 mg orally twice daily, in increments of 12.5 mg, will be considered. The new dosing table and clear instructions on how to handle subjects will be provided to all participating sites by the protocol team via a written notification.

DOSING TABLE 1: 1 year – 6 years

Etravirine (ETR) dose per weight band				
Weight Band (kg)	Dose (mg/kg)	Dose (mg)	Number of Tablet(s) to Administer Orally per Dose	Frequency
<8	8.8	50 mg	2 x 25 mg tablets	Twice Daily
8-<10	8.8	75 mg	3 x 25 mg tablets	Twice Daily
10-<13	8.8	100 mg	1 x 100 mg tablet	Twice Daily
13-<16	6.8	100 mg	1 x 100 mg tablet	Twice Daily
16-<20	5.2	100 mg	1 x 100 mg tablet	Twice Daily
20-<25	5.2	125 mg	1 x 100 mg tablet PLUS 1 x 25 mg tablet OR 5 x 25 mg tablets	Twice Daily
25-<30	5.2	150 mg	1 x 100 mg tablet PLUS 2 x 25 mg tablets OR 6 x 25 mg tablets	Twice Daily
>=30	5.2	200 mg	2 x 100 mg tablets OR 8 x 25 mg tablets	Twice Daily

DOSING TABLE 2: 2 months to < 1 year

Etravirine (ETR) dose per weight band			
Weight Band (kg)	Dose (mg)	Number of Tablet(s) to Administer Orally per Dose	Frequency
<6	25 mg	1 x 25 mg tablet	Twice Daily
6-<8	37.5 mg	1 and a half scored 25 mg tablets	Twice Daily
8-<10	50 mg	2 x 25 mg tablets	Twice Daily
≥10	75 mg	3 x 25 mg tablets	Twice Daily

Note: as of the age of 1 year, doses should be adjusted according to the specific ETR dosing table for 1 year to 6 years (Dosing Table 1).

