6.7 Etravirine Dose Changes Due to Increases in Body Weight

Confirmed increases in subject's body weight will trigger an ETR dose increase as follows:

- If NO PK directed dose change was made following the day 14 (\pm 4 days) PK visit, i.e., the starting ETR dose from dosing tables provided an adequate AUC_{12h} , then as the subject's weight increases such that it crosses into a higher weight band, the dose will be changed to correspond with the new weight band, consistent with the Dosing Table provided in Appendix III.
- If an individualized PK directed dose change was made following the day 14 (\pm 4 days) PK visit, a dose increase is triggered when the subject's weight has increased by 25% from the weight at the most recent AUC_{12h} evaluation. Contact the protocol team at [contact] for an individualized dosing recommendation based on the subject's pharmacokinetic parameters.

There will be no 12-hour pharmacokinetic studies for dose adjustments due to increase in body weight.

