9.34 Individual Subject Dose Evaluation and Adjustments

Doses of ETR will be adjusted in an individual subject to attain an AUC_{12h} of $< 2350 \text{ ng}\cdot\text{h}/\text{mL}$.

- If the subject's current dose is well tolerated (no toxicity \geq Grade 3) but AUC_{12h} is $< 2350 \text{ ng}\cdot\text{h}/\text{mL}$, then a new dose will be determined by prorating the current dose to attain an AUC_{12h} of approximately $2864 \text{ ng}\cdot\text{h}/\text{mL}$ (the 20th percentile of exposure in adults). The maximum dose increase for the initial PK-guided dose adjustment would be capped at the adult dose of 200 mg twice daily. If a second PK evaluation again reveals an $AUC_{12h} < 2350 \text{ ng}\cdot\text{h}/\text{mL}$, then the dose may be increased above the 200 mg twice daily initial BID cap, again, targeting an AUC_{12h} of approximately $2864 \text{ ng}\cdot\text{h}/\text{mL}$.
- If the subject's AUC_{12h} is $> 4380 \text{ ng}\cdot\text{h}/\text{mL}$ (the median AUC_{12h} value in adults receiving ETR 200 mg twice daily) but current dose is not well tolerated (no toxicity \geq Grade 3) then the dose will be prorated, if possible given available dosage forms to achieve an AUC_{12h} of $4380 \text{ ng}\cdot\text{h}/\text{mL}$. If no dose reduction is possible, then the subject will be discontinued from study treatment.
- If a subject has not achieved an AUC_{12h} of $< 2350 \text{ ng}\cdot\text{h}/\text{mL}$, but is experiencing a Grade 3 or greater toxicity that is deemed probably or definitely related to study drug, that subject will be discontinued from study treatment.

Although ETR displays non-proportional PK, dose adjustments will be prorated on a linear scale using multiples of 12.5 mg (the smallest incremental dose change possible given the available formulations).

Initial PK-guided dose increases will be capped at the adult dose of 200 mg twice daily. However, if after a second PK evaluation the subject's AUC_{12h} has not achieved the minimum target (2350 ng•h/mL), doses may exceed 200 mg twice daily. The core protocol team will communicate all individual dose adjustments to the participating site.

All subjects with an individual dose adjustment (not related to weight gain) will have repeat intensive 12 hour PK evaluations performed between Day 7 to 14 after initiation of the new dose.

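### Appendix III moves every child to Dosing Table 1 at age 1 without exempting those on a PK-individualised dose, whom Section 6.7 takes off the weight-band table

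*Protocol*

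**What the plan says.** Three places in the Protocol set the dose of a Cohort III child who turns 1 on treatment.

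- **Appendix III, note to Dosing Table 2:** "as of the age of 1 year, doses should be adjusted according to the specific ETR dosing table" for ages 1 to 6 years. The trigger is age. Nothing separates children on the table dose from children on an individualised dose.
- **Section 6.7:** the trigger is weight, and there are two groups. For a child with no PK-directed change after the Day 14 visit, "the dose will be changed to correspond with the new weight band, consistent with the Dosing Table provided in Appendix III". For a child with such a change, "a dose increase is triggered when the subject's weight has increased by 25" percent since the latest AUC12h evaluation, and the site contacts the team "for an individualized dosing recommendation based on the subject's pharmacokinetic parameters". No 12-hour PK study follows a weight-driven change.
- **Section 9.34:** if the dose is tolerated but AUC12h is below 2350 ng·h/mL, "then a new dose will be determined by prorating the current dose to attain an" AUC12h of about 2864. If AUC12h is above 4380 and the dose is not well tolerated, the dose is prorated down towards 4380. Proration is linear, in 12.5 mg steps. On follow-up: "All subjects with an individual dose adjustment (not related to weight gain) will have repeat intensive 12 hour PK evaluations".

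The SAP does not address the change at age 1.

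**The concern.** An individualised dose exists because the table dose gave that child too little exposure or was not tolerated. If the note is applied as written, a table dose replaces it at the first birthday. No passage says that these children are exempt, that the note yields to 6.7, or that the change is checked by PK sampling.

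An infant reduced for poor tolerance could then receive more than the dose that was not tolerated. An infant raised for low exposure could fall back below the trial's own threshold. Individual adjustment is a realistic event: Section 1.32 reports that 2 of the first 6 children had a PK-directed increase, although these were Cohort I children on the earlier 5.2 mg/kg dose.

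**Working it through.** **1. Who meets the note.** Cohort III enters at 2 months to under 1 year. The longest wait to the first birthday is 10/12 × 365.25 / 7 = 43.5 weeks, so every Cohort III child still on etravirine at Week 48 has met it.

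**2. Size of the switch at unchanged weight.** Doses are from Appendix III (mg twice daily). The AUC limit is the AUC12h on the Table 2 dose below which the Table 1 dose still projects under 2350: limit = 2350 × (Table 2 dose / Table 1 dose). The last two columns take a child reduced by one 12.5 mg step.

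| Weight (kg) | Table 2 | Table 1 | Ratio | AUC limit | Reduced dose | Table 1 / reduced |
|---|---|---|---|---|---|---|
| <6 | 25 | 50 | 2.0 | 1175 | 12.5 | 4.0 |
| 6-<8 | 37.5 | 50 | 1.33 | 1762 | 25 | 2.0 |
| 8-<10 | 50 | 75 | 1.5 | 1567 | 37.5 | 2.0 |
| 10-<13 | 75 | 100 | 1.33 | 1762 | 62.5 | 1.6 |

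In every band the Table 1 dose exceeds the Table 2 dose, so it exceeds any dose reduced below Table 2. That result needs no PK assumption. The AUC limits do: they use the protocol's linear proration and hold weight and clearance fixed.

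**3. Upward adjustments at 8-<10 kg, starting from 50 mg (assumed AUCs).**
- AUC 1400: 50 × 2864/1400 = 102, so 100 mg, projecting 1400 × 100/50 = 2800. Table 1 gives 75 mg, projecting 1400 × 75/50 = 2100, below 2350.
- AUC 1600: Table 1 projects 1600 × 75/50 = 2400, above 2350.
- AUC 2000: 50 × 2864/2000 = 71.6, so 75 mg, the same as Table 1.
- AUC 2200: 50 × 2864/2200 = 65.1, so 62.5 mg. Table 1 is higher.

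The note therefore undoes the adjustment only for markedly low AUCs.

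**4. A downward adjustment with growth (assumed weights and AUC).** A 7 kg infant has AUC 6000 on 37.5 mg (37.5/7 = 5.4 mg/kg), not tolerated. Proration gives 37.5 × 4380/6000 = 27.4, so 25 mg (3.6 mg/kg). At the first birthday the child weighs 9 kg, a gain of 2/7 = 29%. Section 6.7 sends the site to the team for an individual dose. The note gives 75 mg (75/9 = 8.3 mg/kg), above the mg/kg dose that was not tolerated. Both rules apply and they differ.

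**5. Below 25% gain.** Section 6.7 triggers no increase and is otherwise silent on that child. The note still changes the dose.

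**6. Repeat PK.** Section 9.34 exempts changes related to weight gain, and 6.7 rules out PK studies only for those. A change driven by age is not named in either place.

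**The case against.** Section 6.7 concerns weight and the note concerns age. A reader might infer that the two contradict each other for every individualised child. They do not: 6.7 does not make a 25% gain the only possible reason for a change, so below that gain it is silent at age 1. This stands, and it limits the direct conflict to children who have gained 25%.

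Sites do not act alone. Section 6.2 has the team recommend all dose modifications, and 9.34 has it communicate all individual adjustments. This lowers the risk, but the team works from the same two unreconciled rules.

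A reader might also infer that an infant with Grade 3 toxicity would be reduced and then sent above the dose that caused it. The documents do not clearly support that case. Section 6.8 lists related or possibly related Grade 3 events as grounds for stopping etravirine. The 9.34 reduction bullet says the dose is not well tolerated, yet its bracket reads as excluding Grade 3 or higher. Section 8.631 does foresee children whose doses were reduced for toxicity, so a reduced child who stays on treatment is possible; the grade is unclear.

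The step up may be intended. Section 1.32 describes a 25% cut for ages 6 months to under 1 year because enzymes may still be maturing, and lifting it is 1/0.75 = 1.33, which matches two of the four bands. That explains the step for table-dosed infants, but not for a dose derived from the child's own AUC. Growth, maturation and the non-proportional PK noted in 9.34 do make the AUC projections rough; growth and maturation would lower them.

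Finally, Appendix IC ties repeat intensive PK to adjustments for low or high AUC, so a birthday move is naturally read as outside it. The repeat-PK point is therefore an omission, not a contradiction.

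**Conclusion.** The concern holds in this limited form. The age-1 note has no exception for individualised children. It conflicts directly with 6.7 once 25% weight gain has occurred, and acts where 6.7 is silent before that. Followed literally, it overrides every reduction below the Table 2 dose. It returns a child to AUC12h below 2350 only under the limits of about 1175, 1762, 1567 and 1762 ng·h/mL by ascending weight band, under linear PK with weight and clearance fixed.

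The affected group is the individualised part of a cohort planned at 12; the documents give no expected count.

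A reader might infer that the primary Week 48 safety result is distorted. Section 8.631 does not support that: children adjusted for inadequate PK are excluded, and those reduced for toxicity already count as failures. What remains is mainly individual safety and exposure, with possible effects on virology, population PK and the secondary safety analyses. Section 8.1 breaks the latter down by dose period for adjusted children.

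**What to change.** Reconcile the Appendix III note with Sections 6.7 and 9.34. State in each place:

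- which rule governs at age 1 for a child whose dose was changed for PK or tolerance;
- whether the change at age 1 requires repeat intensive PK.

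Also reconcile the bracket on Grade 3 toxicity in the 9.34 reduction bullet with the discontinuation criteria in 6.8, so that it is clear which children can be on a reduced dose. The protocol team decides which rule applies; no dose or rule is proposed here.

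The cost is a short clarification. It could go to sites by written notification, the route that 9.351 and Appendix III already use for starting-dose changes. It needs no new subjects; any added sampling would depend on the team's decision about repeat PK.
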